| 7.1 STATISTICAL DESIGN..... | 34 |
| 7.2..... | 34 |
| 7.3 MISSING DATA | 35 |
| 7.4 DATA QUALITY, ANALYSIS PLAN..... | 35 |
| 8 DATA AND SAFETY MONITORING PLAN (DSMP) | 35 |
| 8.1 STUDY TEAM..... | 35 |
| 8.2 QUALITY ASSURANCE | 36 |
| 8.3 CLINICAL TRIALS OFFICE | 36 |
| 8.4 DSMC..... | 36 |
| 9.2 REGULATORY COMPLIANCE | 37 |
| 9.3 PRESTUDY DOCUMENTATION..... | 37 |
| 9.4 INSTITUTIONAL REVIEW BOARD..... | 37 |
| 9.5 SUBJECT CONFIDENTIALITY AND ACCESS TO SOURCE DOCUMENTS/DATA..... | 38 |

[figure not shown]
| | |
|--|-----------|
| 9.6 PROTECTION OF HUMAN SUBJECTS | 39 |
| 9.6.1 Protection from Unnecessary Harm | 39 |
| 9.6.2 Protection of Privacy | 39 |
| 9.7 CHANGES IN THE PROTOCOL | 39 |
| 9.8 INVESTIGATOR COMPLIANCE | 40 |
| 10 DATA HANDLING AND RECORD KEEPING | 40 |
| 10.1 OVERVIEW..... | 40 |
| 10.2 DATA MANAGEMENT RESPONSIBILITIES | 40 |
| 10.2.1 Principal Investigator | 40 |
| 10.2.2 Research Coordinator | 40 |
| 10.2.3 Research Nurse/Medical Staff | 40 |
| 10.2.4 Biostatistician | 40 |
| 10.3 HANDLING AND DOCUMENTATION OF CLINICAL SUPPLIES | 40 |
| 10.4 SOURCE DOCUMENTS | 41 |
| 10.5 CASE REPORT FORMS..... | 41 |
| 10.6 STUDY RECORD RETENTION | 42 |
| APPENDIX 1. PERFORMANCE STATUS CRITERIA | 43 |
| APPENDIX 2. STUDY DIARY | 44 |
| APPENDIX 3: SUBJECT LOST TO FOLLOW-UP LETTER..... | 47 |
| REFERENCES | 48 |

PROTOCOL SUMMARY

| | |
|----------------------------------|--|
| Title | Inhibition of Oral Tumorigenesis by Antitumor B |
| IND Sponsor | Sponsor Investigator |
| Principal Investigator | [name] |
| Study Sites | Froedtert & the Medical College of Wisconsin |
| Clinical Trial Phase | Phase 0 |
| Study Disease | Oral cavity squamous cell cancer |
| Main Eligibility Criteria | 
 1. Clinical diagnosis of oral cavity squamous cell cancer. 2. Patient can start study agent administration but histological confirmation of squamous cell cancer (SCC) of the oral cavity (or histologic variants of SCC) by the pathologist must happen within seven days of registration in order to continue protocol therapy. 3. Clinical stage I-IVA (as defined by the AJCC, 8th Edition) and amenable to surgical resection. 4. New diagnosis of oral SCC, new second primary, or recurrent oral SCC following a minimum remission of six months following previous definite surgery. 5. Zubrod/ECOG Performance status ≤ 2. 6. Age ≥ 18 years. |
| Primary Objective | To determine the antiproliferative effects of ATB versus placebo as determined by tumor Ki-67. |
| Secondary Objectives | 
 1. Characterize the pharmacokinetics (PK) and pharmacodynamics (PD) properties 2. Determine the biologic correlates of response including NFkB, and RNASeq. |
| Primary Endpoint | Determine the anti-proliferative effects of ATB as determined by tumor Ki-67 in baseline tumor biopsy compared to resected control tumor tissue from untreated patients. |
| Secondary Endpoints | 
 1. PK and PD properties from the saliva samples collected during the period of the study will be calculated. 2. Measure biologic correlates of response including NFkB, and RNASeq from the tumor specimens collected at baseline and on the day of surgery. |
| Study Design | 
This is a window of opportunity study of ATB.
 
The study has been amended from a randomized study of ATB versus placebo to a single arm open label trial of ATB
 |

| | |
|---|--|
| | Upon initiating study treatment, patients will start taking the study drug. The duration of treatment will depend upon scheduling of their surgery—typically from the time surgery is scheduled it will be between seven to 28 days. Four (300 mg) pills will be taken three times per day until the evening prior to surgery. |
| Number of Subjects | Approximately *** subjects will be enrolled to achieve 14 total ATB-treated patients. |
| Estimated Time to Complete Enrollment: | Approximately two years. |

STUDY SCHEMA

STUDY CALENDAR:

| Procedure | Screening ¹ | ATB Administration: (Daily until Day -1 of Surgery) | | End of Treatment | |
|---|--|--|------------------------------------|------------------|-------------------------|
| Study Day/Visit Day | Day – 28 to Enrollment | Day 1 | Prior to Surgery ^{12, 13} | Day of Surgery | Follow Up ¹³ |
| Informed Consent | X | | | | |
| AE Reporting | Recorded from day 1 of the study drug through 30 days after the last dose of study drug (Section 6). | | | | |
| Concomitant Medications ³ | Recorded from signing of the ICF through 30 days after the last dose of study drug. | | | | |
| Physical Exam ² | X | | | X | X |
| Medical History ² | X | | | | |
| Pregnancy Test (Serum or Urine) ^{4, 13} | X | | | | |
| ECOG Performance Status ⁵ | X | | | | |
| Vital Signs per institutional standards | X | | | | |
| Complete metabolic panel ^{6,13} | X | | X | | X |
| CBC w/ Diff and platelet count ¹³ | X | | X | | |
| PT, INR ¹³ | | | X | | |
| Research saliva samples ⁷ | | See footnote 7 for research saliva sample draw timepoints. | | | |
| Tumor Measurement by Physical Exam | X | | | | |
| Tumor Specimen ⁹ | X | | | X ⁸ | |
| CT ^{9, 8} | X | | X | | |
| MDASI-HN (MD Anderson Symptom Inventory-Head and Neck Survey) ¹³ | | X | X | | |
| ATB administration | | Patient to take as directed from day 1-prior to surgery | | | |
| Patient Diary ¹¹ | | X | X | | |

1. Screening procedures must occur within 28 days prior to registration. ATB administration should start within seven days of registration.
2. Focused physical examination by a study investigator.
3. Capture medications taken from signing of informed consent document until 30 days post last dose of ATB. Medications given during the surgical hospitalization will only be collected if related to Adverse event treatment.
4. For women of childbearing potential.
5. Refer to Appendix 1.
6. Including albumin, total protein, total bilirubin, direct bilirubin, ALT, AST, LDH, alkaline phosphatase, bicarbonate, sodium, potassium, chloride, creatinine, , calcium, BUN, and glucose.
7. A total of at least two patient samples (saliva) per day will be collected (predose, before lunch, or before dinner dose 1, dose 2, dose 3 of study drug). Saliva samples will be collected in a 5-ml bio vial, time documented by the patient, then frozen and stored by the patient until collection (see Section 3.1 for more details).
8. Fresh frozen tumor specimen will be collected, see section 5.6 for processing.
9. CT at baseline may be performed within six weeks prior to study registration. CT at day -1 of surgery can have a window of - 3 days. If baseline tumor is not measurable by baseline imaging (eg due to dental artifact) then follow-up imaging is NOT required
10. Patient will complete study diary with all relevant information and will submit the diary to study coordinator on the day of surgery.
11. The date for follow-up assessment is at the discretion of the surgeon and will correspond with the first post-operative outpatient assessment.
12. The indicated assessment for this timepoint will be collected only once with a window of two days: Day -3 to Day 0 of surgery.
13. In special cases and with study team approval, subjects may be able to have imaging, lab work, and completion of surveys completed at specific community sites. This would be done instead of being required to perform these procedures at MCW/FH. They would have to travel to MCW/FH at times for all other procedures and visits.

LIST OF ABBREVIATIONS

| | |
|-------|--|
| AE | adverse event |
| ALP | alkaline phosphatase |
| ALT | alanine aminotransferase |
| ANC | absolute neutrophil count |
| AST | aspartate aminotransferase |
| ATB | antitumor B |
| AUC | area under the curve |
| BUN | blood urea nitrogen |
| CBC | complete blood cell (count) |
| COPD | chronic obstructive pulmonary disease |
| CR | complete response |
| CRC | clinical research coordinator |
| CrCl | creatinine clearance |
| CRF | case report form |
| CT | computerized tomography |
| CTCAE | Common Terminology Criteria for Adverse Events |
| CTO | clinical trials office |
| DFS | disease-free survival |
| DLT | dose-limiting toxicity |
| DSMC | Data and Safety Monitoring Committee |
| DSMP | data and safety monitoring plan |
| FDA | Food and Drug Administration |
| GCP | good clinical practice |
| HCT | Hematocrit |
| HNC | head and neck cancer |
| HNSCC | head and neck squamous cell carcinoma |
| HPV | human papilloma virus |
| ICF | informed consent form |
| ICH | International Conference on Harmonisation |
| IND | Investigational New Drug |
| IRB | Institutional Review Board |
| LDH | lactate dehydrogenase |
| MCWCC | Medical College of Wisconsin Cancer Center |
| NCI | National Cancer Institute |

| | |
|--------|--|
| ORR | overall response rate |
| PBMC | peripheral blood mononuclear cells |
| PD | disease progression |
| PK | Pharmacokinetics |
| PR | partial response |
| RBC | red blood cell (count) |
| SAE | serious adverse event |
| SCC | squamous cell carcinoma |
| SD | stable disease |
| SD | standard deviation |
| SOP | standard operating procedure |
| SRC | Scientific Review Committee |
| TLC | thin layer chromatography |
| ULN | upper limit of normal |
| UP | unanticipated problem |
| UPIRSO | unanticipated problems involving risks to subjects or others |
| WBC | white blood cell (count) |
| WOO | window of opportunity |

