4.1 Subject Status

Subject statuses throughout the trial are defined as follows:

- Prescreening: pre-consent (subject considering trial or study staff considering patient for the trial per institutional recruitment methods).
- Screening: period after consent, but prior to eligibility confirmation.
- Consented: consented, prior to eligibility confirmation.
- Eligible: the local investigator confirms all eligibility criteria apply.
- On study/enrolled: date eligibility is confirmed.

- On arm: date of enrollment.
- On treatment: first day treatment was given to the last day treatment was given.
- Off treatment: the last day treatment was given.
- On follow-up: from last day of treatment to the end of follow-up period.
- Off study: follow-up period completed, with no additional data gathered.
- Withdrawn: subject fully withdraws consent (i.e., refuses ALL follow-up, even survival) or is taken off study by the local PI.

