4.3 Consent

Investigators or their appropriate designees will identify potentially eligible subjects from their clinics, subject self-referrals, referrals from other clinicians and/or other IRB-approved recruitment methods. No study conduct, including subject prescreening, can occur until after IRB approval.

A written, signed informed consent form (ICF) must be obtained before any study-specific assessments are initiated. A signed ICF copy will be given to the subject and a copy will be filed in the medical record (per local IRB policies and SOPs). The original will be kept on file with the study records.

After consent, an OnCore® new subject entry must occur within 24 hours of consent.

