4.4 Screening Procedures

Refer to the study calendar of events.

Visit procedures that were performed as standard of care prior to consent (without the specific intent to make the subject eligible for the trial), may count toward screening tests and eligibility if they are within the screening window.

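### The only scheduled pregnancy test has no window of its own and may fall nominally 35 days before the first ATB dose

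*Combined protocol and SAP*

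**What the plan says.** The Study Calendar marks the serum or urine pregnancy test once, under Screening. The cells for Day 1, Prior to Surgery, Day of Surgery and Follow Up are blank. Two footnotes are attached to the test, and neither sets a time. Footnote 4 says who is tested: "For women of childbearing potential". Footnote 13 says where it may be done: in special cases, with study team approval, "subjects may be able to have imaging, lab work, and completion of surveys completed at specific community sites".

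The general rule in footnote 1 therefore applies: "Screening procedures must occur within 28 days prior to registration. ATB administration should start within seven days of registration".

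Other sections bear on the point:

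- Section 4.1 fixes enrolment: "On study/enrolled: date eligibility is confirmed".
- Section 4.3 says that written consent "must be obtained before any study-specific assessments are initiated".
- Section 4.4 says that routine-care procedures done before consent, without the aim of making the patient eligible, "may count toward screening tests and eligibility if they are within the screening window".
- Section 4.5, inclusion criterion 13, asks a woman of childbearing potential either to use two contraceptive methods or to practise true abstinence. The contraception option runs from consent to 21 days after the last dose. The abstinence option gives no dates.
- Section 4.5, exclusion criterion 1, bars pregnant women because the risk to the embryo or fetus cannot be foreseen. The same section allows no eligibility waivers.
- Section 6.1.2 includes pregnancy in its list of SAE outcomes.

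**The concern.** The protocol treats fetal exposure to ATB as a risk to be avoided, yet the one laboratory check that supports the exclusion may be several weeks old when dosing starts. Eligibility is settled at enrolment, and the calendar does not check pregnancy again between that date and the first dose.

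Two situations would go unnoticed by any scheduled procedure: a pregnancy too early for the Screening test to detect, and a conception between the test and the first dose. Where a pre-consent test is accepted under 4.4, part of that interval may also lie before the contraception period in criterion 13 begins.

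Other baseline items do have their own windows: renal function is tied to 14 days before registration (4.5, criterion 9) and the baseline CT to six weeks (footnote 9). Setting one for the pregnancy test would follow the protocol's own practice.

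**Working it through.** The plan states no total interval from pregnancy test to dosing, so there is no figure to reproduce. The interval follows from the windows.

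**Inputs**

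- Test to registration: 0 to 28 days (calendar footnote 1).
- Registration to first dose: 0 to 7 days, worded as *should* (calendar footnote 1).
- Length of dosing: at most 28 days (5.1, note to the regimen table). The last dosing day is then 28 − 1 = 27 days after the first.
- Assumption: registration and enrolment are the same date. Footnote 1 counts from the first, and the Screening column header runs to the second.

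**Current plan**

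- Test to first dose, nominal maximum: 28 + 7 = 35 days. If the start slips *d* days beyond the advisory seven, it is 35 + *d*.
- Test to first dose, with the test on the day of registration and a start within seven days: at most 0 + 7 = 7 days.
- Test to last dosing day, nominal maximum: 35 + 27 = 62 days.

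**With a window of 7 days before the first dose**

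- Test to first dose, maximum: 7 days, which is 35 − 7 = 28 days shorter.
- Test to last dosing day, maximum: 7 + 27 = 34 days.

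**Is there another check?** Apart from a regulatory citation in 9.2, pregnancy appears elsewhere only in exclusion criterion 1, which names no test or date, and in the SAE definition. Criterion 13 requires contraception or abstinence, not a test. The protocol text reviewed contains no second test and no separate window.

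**How far does criterion 13 cover the interval?**

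- Study-specific test, contraception option: the test follows consent (4.3) and contraception starts at consent, so the whole interval from test to dosing is covered. What remains is method failure, non-adherence or a false-negative early test.
- Routine-care test counted under 4.4, contraception option: the stretch from test to consent is not covered.
- Abstinence option: no start or end date is given, so the period covered cannot be read from the text.

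**How many women?** The Protocol Summary says that "subjects will be enrolled to achieve 14 total ATB-treated patients", men and women together. Section 7.2 says that patients were treated before this amendment and that an unblinding assessment will settle how many more are needed. The number of women of childbearing potential still to be enrolled is not given, so exposed pregnancies are not estimated.

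**The case against.** The plan is not careless here. It excludes pregnancy, tests the women concerned and requires two contraceptive methods or abstinence. The 35 days arise only if the test falls on the first permitted day and dosing on the last nominal one, and the documents do not show that this is typical. The 4.4 route needs a pregnancy test done for routine care, and nothing says that such tests occur. The trial is small and partly enrolled. No document gives seven days as a standard, and a test seven days before dosing can still miss a very early pregnancy.

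All of this stands, and it limits the weight of the point. It does not remove it, because the schedule permits the long interval and retiming one existing test closes most of it.

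A reader might infer more than the documents support:

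- *That a woman known to be pregnant could be enrolled.* She could not. Exclusion criterion 1 applies whether or not the pregnancy has been recognised, and no waiver is allowed.
- *That the fix cuts the risk by 28/35 = 80%.* That ratio describes a scheduling maximum. Risk also depends on the use and failure of contraception and on test sensitivity, for which the documents give no figures.
- *That participants are never tested again in practice.* The consent form and the Clinical Trials Office SOPs that govern eligibility review are not part of the text reviewed. The supportable statement is that this protocol schedules no later test.

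**Conclusion.** The point holds as a minor, cheap safety improvement. The single Screening test is governed only by the general window, so it may be nominally 35 days old at the first ATB dose, and no scheduled procedure would then find a missed or new pregnancy. Criterion 13 lowers the risk without replacing a test close to dosing.

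The conclusion rests on the calendar as printed, on registration and enrolment being the same date, and on the advisory seven-day start being kept. It is not a major defect: the affected group is limited to women of childbearing potential yet to enrol, and the documents give no basis for estimating the size of that group or the number of exposed pregnancies. The primary Ki-67 analysis is not affected.

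**What to change.** Add a calendar footnote to the pregnancy test: women of childbearing potential need a negative urine or serum test, obtained after consent and within 7 days before the first ATB dose, and ATB is not started if the test is positive. The sponsor or IRB may choose a shorter window. Add one sentence to 4.4 saying that a test done before consent does not meet this requirement. The footnote should also say how a woman is recorded if she is already enrolled and then tests positive before dosing.

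Time the existing Screening test to satisfy the footnote, for example after consent on the day of registration. With a start within the existing seven days, no second test is needed. Repeat the test only if it falls outside the window, including when the start slips.

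The cost is a protocol amendment with IRB approval before implementation (9.7) and one inexpensive extra test for each woman outside the window. The calendar marks no blood or urine test on Day 1, so a repeat would have to be placed at drug pick-up or Day 1. Footnote 13 already allows a community site in special cases. The change shortens the undetected interval without removing it: a very early pregnancy can still be missed, and no test is added during dosing.

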1. BACKGROUND

1.1. Head and Neck Cancer

Head and neck cancer refer to a group of biologically similar cancers originating from the upper aerodigestive tract, including the lips, oral cavity, nasal cavity, paranasal sinuses, pharynx, and larynx. Most head and neck cancers are SCC originating from the flattened epithelium of these regions. Head and neck cancer accounts for about 3–5% of all malignancies in Western countries with cancer of the oral cavity accounting for 30% of all head and neck cancers. Oral cancer is the sixth most frequent cancer in the world and approximately 36,500 new cases are diagnosed and 8,000 patients die annually in the United States from this disease (1). Squamous cell carcinomas (SCC) are the most common malignant neoplasm of the oral cavity. More than 90% of oral cancers are SCC, of which most have premalignant epithelial lesion stages, such as oral leukoplakia and erythroplakia (2, 3). The survival rate of patients with HPV negative and oral cavity SCC of the head and neck (HNSCC) remains poor (4, 5). Despite significant advancements in chemotherapy and radiation therapy, five-year survival rates for these patients have not changed markedly in the past two decades (6, 7). Development of effective chemopreventive interventions of HNSCC is, therefore, urgently needed.

1.2 Chemoprevention: Antitumor B (ATB)

One of the most promising chemopreventive agents to prevent head and neck cancer is Antitumor B (ATB), a Chinese herbal mixture. It is a botanical agent composed of six Chinese herbs: *Sophora tonkinensis*, *Polygonum bistorta*, *Prunella vulgaris*, *Sonchus brachyotus*, *Dictamnus dasycarpus*, and *Dioscorea bulbifera*. ATB is formulated as 300 mg tablets (Table 1) (8), and manufactured in a GMP facility by National Traditional Chinese Medicine Pharmaceutical Engineering Technology Research Center (Shanghai, China). Previously, [name] and [name] were able to secure a 20-kg batch of ATB for their proposed study in a funded NIH grant (NIH AT003203), and as such we are confident that we will again be able to secure a large single batch of ATB, enough for its exclusive use in this grant. ATB appears to be very effective in the chemoprevention of upper aerodigestive tract tumors in humans. In addition, it has been safe in trials using several thousand subjects over a period of more than two decades (9-11). Earlier clinical studies conducted in China showed that use of ATB reduced the cancerization rate of marked esophageal dysplasia by 50% (9-11). In this clinical trial, more than 2,500 cases of marked esophageal dysplasia were randomly divided into groups for ATB and placebo, respectively (9-11). After three or five years of treatment, the progression of esophageal dysplasia to esophageal cancer was inhibited by a remarkable 52.2% and 47.3%, respectively (9-11).

Table 1. Composition of Antitumor B (percent weight)

| Herbal Name | | Form | % Content |
|-----------------------------|---------------|---------------|-----------|
| Latin | Chinese | | |
| Sophora tonkinensis | Shan Dou Gen | Water Extract | 18-24 |
| Polygonum bistorta | Quan Shen | Water Extract | 17-21 |
| Prunella vulgaris | Xia Ku Cao | Water Extract | 18-25 |
| Sonchus brachyotus | Bei Bai Jiang | Water Extract | 17-23 |
| Dioscorea bulbifera | Huang Yao Zi | Water Extract | 3-6 |
| Dictamnus dasycarpus | Bai Xian Pi | Powder | 8-12 |

A randomized study of ATB as a preventive agent in patients with oral leukoplakia. Since oral SCC has etiology, histopathology, and molecular mechanism similar to esophageal SCC, it is likely that ATB may be effective for oral cancer chemoprevention. A recent study by Sun Z *et al.* examined the chemopreventive effects of ATB in a short-term clinical trial of oral leukoplakia (8). In a three-year period, they recruited 120 patients with oral leukoplakia in Beijing, China and

administered them either ATB tablets or placebo tablets orally. The treatment regimen was four (300 mg) tablets each time, three times per day for eight to 12 months. During the entire trial, they conducted clinical evaluations at the study entry time, monthly during the intervention, and three months after the study period; they recorded oral leukoplakia lesions with color photos and measured sizes. They defined a positive response as a disappearance or reduction of size by more than 50% at the final checkup, stable disease as an insignificant change in the size, and progressive disease as an increase in the size of the lesion by >50% or the development of new lesions. In the end, they found that the ATB intervention reduced the size of oral leukoplakia in 40 out of 59 patients, whereas the placebo was effective in nine out of 53 patients (8). The difference was significant ($p < 0.01$). Such an effect was associated with a significant decrease in the labeling indexes of biomarkers of cell proliferation (AgNOR and PCNA) (8).

